9. STATISTICAL CONSIDERATIONS

9.1 Study Design/Endpoints

9.1.1 Study Design

This is a nonrandomized, open label, single institution phase II trial with a safety run-in to evaluate the safety and efficacy of LDFRT plus temozolomide in patients with recurrent HGG previously treated with surgical resection followed by adjuvant radiation therapy plus temozolomide.

The original primary objective of this study was response rate where a CR+PR rate below 10% was considered clinically insignificant whereas a CR+PR rate above 25% was considered clinically significant using the temozolomide re-challenge group B3 of the Perry et al. JCO 2010 study as a comparator.

Response rate was considered an appropriate primary objective since this was considered a predominantly chemotherapy based trial. We did not anticipate radiation-induced MRI changes (pseudo-progression) given the very low doses of radiation that are prescribed in this clinical trial.

As of 2/10/2017, 22 patients had been treated on study. At the time of the interim analysis, there were no clinical responses. Given the unexpected number of patients experiencing pseudo-progression on this study, and the possible implications of this for assessing response rate or progression free survival (PFS), the primary objective of this study is being changed to one year overall survival (OS). The current one year OS is 45.1% (80% CI: 28.2%, 60.9%). The median OS at this time is 9.5 months with a median follow-up of 12.7 months. When stratifying by tumor type there is no statistically significant difference in outcomes by group. The 17 patients with glioblastoma have a 1 year overall survival of 33% (80% CI: 13%-79%) and the 1 year overall survival for the 5 patients with anaplastic astrocytoma is 60% (80% CI: 13%-79%). These data suggest that early termination of the study due to futility is not warranted and support the revision of the primary endpoint to allow completion of the study with the originally intended sample size.

9.1.2 Endpoints

9.1.2.1 Safety Run-In

9.1.2.1.1 Primary Endpoint

Dose-limiting toxicity (DLT) is defined as hematologic toxicity during the month following cycle #1 of temozolomide plus LDFRT grade ≥ 3 by NCI common toxicity criteria version 4. All patients who receive any amount of LDFRT will be evaluable for toxicity. The recommended phase II dose will be the highest dose yields $\leq 33\%$ DLT rate.

9.1.2.1.2 Secondary Endpoint

Radiation-associated neurologic toxicity of LDFRT plus temozolomide using the RTOG/EORTC acute (≤ 3 months) and late (>3 months) radiation morbidity scoring criteria at 3, 6 and 12 months following completion of therapy. Since the total radiation dose to the brain is low and delivered in very small fractions, the likelihood of radiation associated toxicity is expected to be low. The radiation-induced necrosis rate is less than 5% in patients with recurrent gliomas re-irradiated to a median dose of 36 Gy using conventional 2 Gy fractions (Combs JCO 2005). However, we will be collecting late radiation toxicity data and if there are four patients with radiation related symptomatic necrosis believed to be a result of the LDFRT, the trial will be suspended to accrual and a safety review by the institutional DSMB will be requested.

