1.1.2 Secondary Objectives

To estimate the acute and late radiation-associated neurologic toxicity of salvage LDFRT + temozolomide.

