5.3 Duration of Therapy

In the absence of treatment delays due to adverse events, LDFRT will be administered with the first 6 cycles of temozolomide and temozolomide will continue for a total of 1 year and or until one of the following criteria applies:

- Disease progression,
- Intercurrent illness that prevents further administration of treatment,
- Unacceptable adverse event(s),
- Patient decides to withdraw from the study, or
- General or specific changes in the patient's condition render the patient unacceptable for further treatment in the judgment of the investigator.

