8.1 Antitumor Effect

Response and progression will be evaluated in this study using the international criteria proposed by the Response Assessment in Neuro-Oncology Working Group (RANO) (19).

8.1.1 **Definitions**

Evaluable for toxicity. All patients will be evaluable for toxicity from the time of their first treatment with LDFRT.

Evaluable for objective response. Only those patients who have received at least one cycle of therapy, and have had their disease re-evaluated will be considered evaluable for response. These patients will have their response classified according to the definitions stated below. (Note: Patients who exhibit objective disease progression prior to the end of cycle 1 will also be considered evaluable.)

8.1.2

8.1.3 **Methods for Evaluation of Disease**

All baseline evaluations should be performed as closely as possible to the beginning of treatment and never more than 4 weeks before the beginning of the treatment.

The same method of assessment and the same technique should be used to evaluate patients at baseline and during follow-up. Imaging-based evaluation is preferred to evaluation by clinical examination when both methods have been used to assess the antitumor effect of a treatment.

MRI: T1 with gadolinium, T2 and FLAIR sequence MRI techniques should be performed with cuts of 5 mm or less in slice thickness contiguously.

Corticosteroid use: Dosages of corticosteroids will be recorded at baseline as well as follow-up visits and will be incorporated into the response criteria.

Clinical examination: Neurologic deficits and symptoms will be recorded at baseline as well as follow-up visits and will be incorporated into the response criteria.

8.1.4 **Progression-Free Survival**

Progression free survival will be measured from the date of initiation of salvage treatment to the date of documented progressive disease according to the RANO criteria (19).

8.1.5 **Overall Survival (OS)**

OS is defined as the duration of time from start of treatment to time of death from any cause.

8.1.6 **Pseudo-progression**

September 29, 2022

Pseudo-progression will be defined and MRI changes including T1 post-gadolinium, T2 or T2 variants such as FLAIR imaging, with or without clinical deterioration and/or increase in dexamethasone dose which stabilizes or reverses on later evaluations without a change in oncologic intervention.

8.1.7 **Toxicity**

Toxicity will be monitored according to the criteria outlined in section 5.2.1.

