9.3 Statistical Methods of Analysis

9.3.1 **Safety/Toxicity:** NCI CTC version 4.0 will be used for scoring the toxicity and adverse events. The severity and frequency of the toxicity will be tabulated by the tested dose or doses using descriptive statistics. The proportions of patient who experienced grade 3 or above toxicities will be estimated, along with 95%

confidence intervals by each type of toxicity.

9.3.2 Pseudo-progression: The proportion of patients who had pseudo-progression will be reported with 95% confidence intervals.

9.3.2 PFS-6: The definition of progression will be based on RANO criteria (19). Progression free will be measured from initial salvage starting date to the date of progressive disease is defined (documented). The proportion of PFS-6 will be estimated along with 95% confidence intervals using the exact binomial method.

9.3.3 OS: the survival time is defined from the date of treatment start to the date of death. Patients who have not died by the analysis data cut-off date will be censored at their last date known to be alive. The Kaplan-Meier method will be used to estimate one year survival, and median survival along with 80% confidence intervals.

9.3.4 Radiation Toxicity: descriptive statistics will be used to summarize radiation toxicity based on the RTOG/EORTC acute and late radiation morbidity scoring criteria (see appendix B and C) for all patients who had any radiation treatment in this study.

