	Wk 25	Wk 26	Wk 27	Wk 28	Wk 29	Wk 30	Wk 31	Wk 32	Wk 33	Wk 34	Wk 35	Wk 36	Wk 37	Wk 38	Wk 39	Wk 40	Wk 41	Wk 42	Wk 43	Wk 44	Wk 45	Wk 46	Wk 47	Wk 48	3 MFU	6 MFU	12 MFU⁶	
Temozolamide	X				X				X					X				X				X						
Interval medical history	X				X				X					X				X				X				X	X	X
Physical exam																										X ⁴	X ⁴	X ⁴
Performance status	X				X				X					X				X				X				X	X	X
CBC with diff¹	X				X				X					X				X				X				X	X	X
CMP¹	X				X				X					X				X				X				X	X	X
NCI Common Toxicity Criteria	X				X				X					X				X				X						
RTOG Acute/Late Morbidity Criteria²	X				X				X					X				X				X				X	X	X
MRI³								X									X								X	X	X	X

¹Laboratory tests will be requested and performed at the discretion of the patient's medical oncologist.

²Use RTOG Acute Toxicity Criteria during RT and for first 6 months following completion of RT. Use RTOG Late Toxicity Criteria at baseline and at scheduled intervals 6 months following completion of RT.

³MRI imaging will be performed approximately every 2 months during temozolamide and then according to the schedule outlined above. MRI sequences must include at a minimum T1 with gadolinium, T2 and FLAIR sequences. Other sequences may be obtained at the provider's discretion. An MRI which is delayed or missed as a result of the deterioration of the patient's clinical condition or other adversity will not be considered a protocol violation.

⁴The physical exams at follow-up may be focused neurological examinations

⁵Follow-Up appointments are permitted a +/- 10 day tolerance window

September 29, 2022

⁶Continue patient follow-up with interval histories and MRI until the time of patient death. After 12 months following completion of temozolomide, follow-up histories and imaging will be at the provider's discretion.

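### The run-in neurologic endpoint names only post-therapy readings, so as worded it does not use the on-treatment RTOG acute scores that its acute objective needs

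*Combined protocol and SAP*

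**What the plan says.** - **Objective.** Section 1.1.2 sets the run-in secondary objective: "To estimate the acute and late radiation-associated neurologic toxicity of salvage LDFRT + temozolomide".
- **Endpoint.** The run-in Section 9.1.2.1.2 uses the RTOG/EORTC acute (up to 3 months) and late (beyond 3 months) "radiation morbidity scoring criteria at 3, 6 and 12 months following completion of therapy". It names no on-treatment reading and does not say which therapy must be complete.
- **Treatment length.** Section 5.3: "LDFRT will be administered with the first 6 cycles of temozolomide and temozolomide will continue for a total of 1 year".
- **Calendar.** Appendix D marks RTOG scoring at baseline, in each of cycles 1–6, in cycles 7–12, and at 3, 6 and 12 months of follow-up. Its RTOG footnotes apply the acute scale during radiotherapy and for 6 months after it. The three follow-up columns come after week 48, and the footnote to the 12-month column counts from the end of temozolomide: "After 12 months following completion of temozolomide, follow-up histories and imaging will be at the provider's discretion".
- **Analysis.** Section 9.3.4 summarises RTOG acute and late toxicity descriptively "for all patients who had any radiation treatment in this study". It sets no visits, no acute window and no per-patient summary.
- **Evaluability.** Section 8.1.1: "All patients will be evaluable for toxicity from the time of their first treatment with LDFRT".
- **Phase II.** The phase II RTOG endpoint, in the later section that repeats the number 9.1.2.1, has no time restriction.

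**The concern.** The objective has an acute half, and the endpoint written for it starts reading 3 months after therapy ends. The scores that measure acute reactions, taken cycle by cycle while LDFRT is given, are in the calendar but not in the endpoint definition. An analyst who follows Section 9.1.2.1.2 to the letter would report acute neurologic toxicity without them. Anyone whose event cleared, or who died, before the first reading would contribute no event, and the acute rate for this endpoint would come out too low.

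Neurologic events did occur. Section 2.3 reports aphasia and cognitive disturbance, in one patient each, among the serious events attributed to treatment in the first 22 patients. It does not say when they occurred.

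**Working it through.** **1. Timing of the first reading (no survival assumption).**

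Months are 365.25/12 = 30.44 days.
- Last LDFRT: cycle 6 starts after 5 × 28 = 140 days. Five treatment days bring it to day 145, and 145/30.44 = 4.76 months.
- End of 12 temozolomide cycles: 48 × 7 = 336 days, and 336/30.44 = 11.04 months.
- First reading on the temozolomide clock: 11.04 + 3 = 14.04 months. That is 14.04 − 4.76 = 9.28 months after the last LDFRT.
- First reading on the LDFRT clock: 4.76 + 3 = 7.76 months.

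Counted from the end of radiation, 9.28 months is beyond both the 3-month cut in Section 9.1.2.1.2 and the 6-month cut in Appendix D. A patient completing the year would then have no acute-scale reading among the three. On the LDFRT clock, the first reading falls exactly on the 3-month boundary. On neither clock does a reading fall during LDFRT.

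**2. Share of patients alive at the first reading.**

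The documents give no figure for this. The inputs are the interim results from 22 patients. Section 9.1.1 says "The median OS at this time is 9.5 months with a median follow-up of 12.7 months" and gives one-year OS as 45.1% (80% CI 28.2% to 60.9%). Section 9.2.1.2 gives one-year OS as 41.5%. Section 2.3 gives median PFS as 4.0 months.

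Assume exponential survival: S(t) = 0.5^(t/9.5), or S(t) = S(12)^(t/12).

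Consistency check: 0.5^(12/9.5) = 41.7%. This is close to 41.5% and 3.4 points below 45.1%. The Kaplan-Meier estimates themselves cannot be reproduced without patient data.

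| Meaning of the end of therapy | First reading (months) | From median 9.5 | From 45.1% | From 41.5% |
|---|---|---|---|---|
| 12 temozolomide cycles | 14.04 | 35.9% | 39.4% | 35.7% |
| One calendar year of temozolomide | 15.00 | 33.5% | 37.0% | 33.3% |
| Last LDFRT fraction | 7.76 | 56.8% | 59.7% | 56.6% |
| Stop at median PFS (4.0 months) | 7.00 | 60.0% | 62.8% | 59.9% |

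The 80% limits for one-year OS give, at 14.04 months, 0.282^(14.04/12) = 23% and 0.609^(14.04/12) = 56%.

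**3. Whose clock the month-14 figure uses.**

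Month 14 applies to a patient who completes the temozolomide year and so is alive at month 11. Under the same model, 0.5^(3/9.5) = 80% of such patients reach the 3-month visit. If PFS is also exponential, only 0.5^(11.04/4.0) = 15% are progression-free at 48 weeks, and Section 5.3 ends treatment at progression. Most patients would therefore run on an earlier clock if stopping early counts as completing therapy.

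**The case against.** The strongest reply is that the gap lies in one sentence, not in the trial. Section 9.1.2.1.2 does not say that its readings are the only ones, and Appendix D prescribes acute-scale scoring during radiotherapy. Section 9.3.4 summarises all irradiated patients without limiting visits. The phase II RTOG endpoint is likewise unrestricted, and Section 9.2.1.2 counts the six run-in patients at the selected dose toward phase II. Section 10.2 records all radiation-related adverse events. Run-in dose selection rests on hematologic toxicity alone, and Section 2.3 says that this stage is finished.

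All of this stands as an answer to a stronger reading, that acute neurologic toxicity goes unrecorded or that the trial's overall toxicity report rests on survivors. The documents do not support that reading.

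It does not repair the endpoint. Section 9.3.4 has no acute window and no worst-grade rule, so it cannot tell an analyst how to form the acute half of objective 1.1.2. Section 9.1.2.1.2 is the only place that sets time points for it.

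A reader might also infer that only about a third of patients live to the first reading. That figure applies the full-year completer's clock to every patient from the start of treatment and needs an interpretation that Section 9.1.2.1.2 does not state. The calendar columns favour the end of temozolomide, but the RTOG footnotes count from the end of radiotherapy.

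**Conclusion.** The endpoint wording does not match its objective or the calendar and should be corrected. Read literally, Section 9.1.2.1.2 uses none of the per-cycle acute scores. On the calendar's temozolomide clock, a patient completing the year is first read about 9 months after the last LDFRT, outside either acute window. That result follows from the schedule alone.

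The survival figures are illustrative. They assume an exponential curve and borrow interim results from 22 patients rather than from the six-patient run-in. They run from about 36–39% alive (12-cycle temozolomide clock) to 57–60% (LDFRT clock) and 60–63% (stop at the median PFS), so no single figure should be attached to this point. Section 5.5 also does not say whether RTOG scoring continues after removal from study, so being alive at a reading does not guarantee a score.

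The consequence is limited to how this one secondary endpoint is reported. No dose decision depends on it, and the underlying scores are scheduled.

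**What to change.** In Sections 9.1.2.1.2 and 9.3.4, define acute neurologic toxicity as the worst RTOG acute CNS grade per patient over all scheduled assessments from the first LDFRT fraction to the end of the acute window, in all patients who received any LDFRT. Keep the 3, 6 and 12 month readings for late toxicity.

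State what counts as the end of therapy. Reconcile that definition, and the acute/late cut (3 months in Section 9.1.2.1.2, 6 months in Appendix D), between the two places without changing the visit schedule.

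The cost is endpoint and analysis wording only: the assessments are already in Appendix D, and no visit is added or moved. The one downside is that the reported acute toxicity rate may be higher.

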9.1.2.1 Phase II

Amended Primary Objective: Estimate one year OS in patients treated with LDFRT + temozolomide for recurrent GBM.

9.1.2.1.1 Primary Endpoint: OS will be measured from initial salvage starting date to the date of death.

9.1.2.1.2 Secondary Endpoints:

9.1.2.1.1.1 **PFS-6:** The definition of progression will be based on RANO criteria (19). Progression free will be measured from initial salvage starting date to the date of progressive disease is defined (documented).

9.1.2.1.1.1.1 Occurrence of pseudoprogression at any time point will be recorded as a binary variable for each patient (yes/no)

9.1.2.1.1.1.2

Use NCI common toxicity criteria (version 4, see section 5.2.1) to record the toxicity of LDFRT plus temozolomide for each patient associated with the treatment. All patients who receive any amount of LDFRT will be evaluable for toxicity.

1.2.1.1.1.3 Use the RTOG/EORTC acute and late radiation morbidity scoring criteria (see appendix B and C) to record the toxicity of LDFRT plus temozolomide for each patient with recurrent HGG. All patients who receive any amount of LDFRT will be evaluable for toxicity.

9.1 Sample Size/Accrual Rate

9.2.1 Sample Size

9.2.1.1 Safety run-in

A minimum of 6 and up to 24 patients will be enrolled for the safety run-in study at an accrual rate of 1 patients per month at the starting dose 0.5 Gy twice daily on days 1-5 of temozolomide. The exact number of patients will depend on the number of dose levels in this phase.

9.2.1.2 Phase II

Amended Primary Objective: The amended primary objective of the study is one year OS. The current one year OS after 22 patients have been enrolled and followed for a median of 12.7 months is 41.5% (80% CI: 25%, 68%). The one year OS for the historical reference used for this study, TMZ alone (Perry JCO 2010), was reported as 28.6%.

Claiming improvement in one year OS within the context of a protocol with an amended primary objective would not be justified, however, the lower bound of the current 80% confidence interval is fairly promising compared to the historical estimate. Additional follow-up of the current patients and completing enrollment to the sample size of 31 will allow us to estimate one year OS with greater precision: width of current CI 0.33 versus simulated mean width of 0.23, Table 1. A one year OS with a lower bound of an 80% CI greater than 28% would be considered sufficiently promising for further study.

Table 1. Lower bound and mean width of 80% CI for one year OS based on 500 simulations with a sample size of 31

September 29, 2022

Simulated true 12 mo. OS	Simulations with lower bound > 28.6%	Mean width of 80% CI:
0.30	19.8%	0.21
0.35	38.6%	0.22
0.40	59.0%	0.22
0.47	82.8%	0.23
0.50	93.4%	0.23
0.55	98.0%	0.23

Original Primary Objective: The primary objective of this trial is to evaluate the therapeutic efficacy of LDFRT plus temozolomide in patients with recurrent HGG. A true (partial or complete) response rate below 10% is considered clinically insignificant and a true (partial or complete) response rate above 25% clinically is considered clinically significant. A 2-stage design will be used to follow for early termination if there is strong early evidence to support the null hypothesis that the true response rate is at most 10%. The alternative hypothesis is that the true response rate is at least 25%. A total of 31 patients will yield 80% power to detect a response rate (PR+CR) of 25% compared to a 10% rate among patients treated by TMZ alone (Perry JCO 2010) at a one-side alpha level of 0.1. Note that in this study (Perry JCO 2010) the outcomes for the “rechallenge” GBM group was comparable to the AA group.

In the first stage, if 2 or fewer patients of the first 20 accrued to the study show response (PR+CR), the study will be terminated. Otherwise, the study will continue to a second stage with additional 11 patients to a total of 31 patients. If 6 or more out of the 31 patients had PR or CR, the LDFRT plus temozolomide will be considered efficacious and recommended for future comparative study. The estimated probability of early stopping for null is 68%. The probability of early stopping under the alternative hypothesis is 9%. The 6 patients from the selected phase II dose enrolled in the safety run-in will count towards the phase II trial, so that the minimum number of patient for the study is 31 and the maximum is 49.

Safety Monitoring:

Early stopping for toxicity: according to observed severe adverse event (about 5% necrosis rate) that related to RT from the study with higher RT dose than this study among re-radiation HGG patients (Combs JCO 2005), it is very unlikely this low RT dose study will yield DLTs or later RT toxicity as necrosis. However, the study will monitor SAEs (RT related DLTs or Necrosis) continuously through the trial. Assuming the low dose RT related SAE rate follows a binomial distribution. In general, the trial enrollment will be suspend for safety consultation if a posterior probability of SAE rate exceeding 0.2 is great than 60%. The prior for this monitoring rule is a Beta distribution assuming a mean SAE rate of 5%.

September 29, 2022

The safety stopping rule and the operating characteristics are shown below and there are based on 5000 simulations:

SAE event in 2 out of 3 patients. $\Pr(\text{Risk}>0.2 \mid \text{Data}) = 0.6$
SAE event in 3 out of 6 patients. $\Pr(\text{Risk}>0.2 \mid \text{Data}) = 0.7$
SAE event in 4 out of 9 patients. $\Pr(\text{Risk}>0.2 \mid \text{Data}) = 0.76$
SAE event in 4 out of 12 patients. $\Pr(\text{Risk}>0.2 \mid \text{Data}) = 0.62$
SAE event in 5 out of 15 patients. $\Pr(\text{Risk}>0.2 \mid \text{Data}) = 0.69$
SAE event in 6 out of 18 patients. $\Pr(\text{Risk}>0.2 \mid \text{Data}) = 0.74$
SAE event in 6 out of 21 patients. $\Pr(\text{Risk}>0.2 \mid \text{Data}) = 0.63$
SAE event in 7 out of 24 patients. $\Pr(\text{Risk}>0.2 \mid \text{Data}) = 0.69$
SAE event in 8 out of 27 patients. $\Pr(\text{Risk}>0.2 \mid \text{Data}) = 0.74$
SAE event in 8 out of 30 patients. $\Pr(\text{Risk}>0.2 \mid \text{Data}) = 0.65$
SAE event in 9 out of 35 patients. $\Pr(\text{Risk}>0.2 \mid \text{Data}) = 0.64$
SAE event in 10 out of 40 patients. $\Pr(\text{Risk}>0.2 \mid \text{Data}) = 0.63$
SAE event in 11 out of 45 patients. $\Pr(\text{Risk}>0.2 \mid \text{Data}) = 0.62$
SAE event in 13 out of 55 patients. $\Pr(\text{Risk}>0.2 \mid \text{Data}) = 0.61$

Operating characteristics:

Underline true SAE rate	Probability declare unsafe	Average sample size
0.10	3.3	160
0.15	18.4	140
0.20	60.5	91
0.30	99.7	24
0.35	100	17

All SAEs or toxicity events will be tabulated by type and grade based on NCI CTC Version 4.0 for toxicity and adverse events. SAEs with an attribution of possible or above will be evaluated for early stopping. Proportion of individual type of SAE event will be estimated using the binomial distribution along with 95% confidence interval (exact method).

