The phase 1 component of the study is completed and all patients are being treated according to cohort 1. In general patients have tolerated treatment well with 5 patients with SAEs attributable to the study treatment (fatigue in 2 patients, and lymphocytopenia, aphasia, cognitive disturbance each in 1 patient). Two of 22 patients had pathologically confirmed radionecrosis.

This unanticipated pseudo-progression type response renders our original primary objective of response rate inappropriate. With this amendment we wish to change the primary objective to one year overall survival and enroll the remaining nine patients. The current one year OS is 45.1% (80% CI: 28.2%, 60.9%), the median OS is 9.5 months (median follow-up of 12.7 months) and the median PFS is 4.0 months. Given that patients on this trial have been treated without any severe toxicities, it would be informative to determine if it is possible that there may be a delayed treatment effect that would indicate further study was warranted. Since overall survival is the most definitive endpoint for a clinical trial, we would like to estimate this outcome with the full sample size of 31 and potentially use this information as a reference in a future

clinical trial.

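### The amended OS go rule was set with 22 of its 31 patients already seen, but Table 1 gives pass probabilities as if all 31 were unseen, understating the chance of a pass near the historical rate

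*Combined protocol and SAP*

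**What the plan says.** The February 2017 amendment (section 2.3) replaced response rate as the primary objective: "With this amendment we wish to change the primary objective to one year overall survival and enroll the remaining nine patients". Section 9.1.1 dates the look: "As of 2/10/2017, 22 patients had been treated on study". Both sections print the interim result: "The current one year OS is 45.1% (80% CI: 28.2%, 60.9" per cent). Section 9.2.1.2 prints a different one, 41.5% with an 80% interval of 25% to 68%, but gives the width of the current interval as 0.33.

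Section 9.2.1.2 then sets the go rule: "A one year OS with a lower bound of an 80% CI greater than 28% would be considered sufficiently promising for further study". The historical one-year OS on temozolomide alone "was reported as 28.6" per cent. Table 1 is captioned "Lower bound and mean width of 80% CI for one year OS based on 500 simulations with a sample size of 31" and its pass column is headed "Simulations with lower bound > 28.6" per cent. So the threshold is 28% in the rule and 28.6% in the table. No conditioning on the 22 patients is described.

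Section 9.3.3 specifies Kaplan-Meier with 80% intervals and names no transformation. Section 9.2.1.2 also concedes that a claim of improved OS could not be justified after this change of objective, and it supports completing enrolment by the gain in precision.

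**The concern.** The rule will be applied to a pooled 31 patients. When it was written, OS in 22 of them had been examined and only nine were still to be enrolled. A reader of Table 1 would take 19.8% as the chance that a regimen with 30% one-year OS, barely above the historical rate, is sent forward. That figure belongs to a trial in which no outcome is yet known. Here a favourable interim result is already in the pooled estimate, so the chance of a mistaken go near the historical rate is higher than printed. This is the only decision rule attached to the amended primary endpoint.

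**Working it through.** **Inputs.** n = 31, 22 seen and nine new (sections 2.3 and 9.1.1); interim OS 45.1% (28.2-60.9%) or 41.5% (25-68%); threshold 28% or 28.6%; Table 1 (section 9.2.1.2); median follow-up 12.7 months (section 9.1.1); z = 1.2816 for an 80% interval.

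**Step 1: reproduce Table 1.** With complete 12-month follow-up and p = s/31, the log-scale Kaplan-Meier lower bound is p × exp(-z × sqrt((1-p)/(31p))).
- s = 12: 0.387 × exp(-1.2816 × 0.226) = 0.290.
- s = 11: 0.260.

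A pass therefore needs 12 of 31 under either threshold. On the log-log scale, p^exp(z × sqrt((1-p)/(31p))/|ln p|), the bound is 0.276 at 12 and 0.305 at 13, so 13 are needed. Pass probabilities for 31 unseen patients are binomial tails:

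| True OS | Table 1 | P(at least 12 of 31) | P(at least 13 of 31) |
|---|---|---|---|
| 0.30 | 19.8% | 19.2% | 10.7% |
| 0.35 | 38.6% | 39.7% | 26.4% |
| 0.40 | 59.0% | 62.5% | 48.0% |
| 0.47 | 82.8% | 86.6% | 77.1% |
| 0.50 | 93.4% | 92.5% | 85.9% |
| 0.55 | 98.0% | 97.7% | 94.9% |

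The 12-survivor column fits. The 0.40 row is within simulation error: sqrt(0.59 × 0.41/500) = 2.2 points. The 0.47 row is looser, 3.8 points against a standard error of 1.7. The 13-survivor column does not fit. Mean log-scale widths of 0.21 to 0.23 also match. Table 1 is thus an unconditional calculation.

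**Step 2: condition on the 22, treated as complete.** 0.451 × 22 = 9.9, about 10 survivors; 0.415 × 22 = 9.1, about 9. With 12 needed, 2 or 3 of the nine new patients must survive. At OS 0.30, P(Bin(9, 0.30) ≥ 2) = 80.4% and P(≥ 3) = 53.7%.

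**Step 3: allow for incomplete follow-up.** With median follow-up of 12.7 months, some of the 22 may not have reached 12 months. The documents give no individual times. The simulation assumed exponential survival and uniform follow-up (three spreads, about 10 of 22 under 12 months), conditioned on the interim estimate, and followed all 31 to 12 months. Log scale, 12 of 31 needed:

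| True OS | 31 unseen | 10/22 complete | 9/22 complete | 45.1%, incomplete | 41.5%, incomplete |
|---|---|---|---|---|---|
| 0.30 | 19.2% | 80.4% | 53.7% | 51-58% | 39-44% |
| 0.35 | 39.7% | 87.9% | 66.3% | 67-73% | 56-60% |
| 0.40 | 62.5% | 92.9% | 76.8% | 80-84% | 71-74% |
| 0.47 | 86.6% | 97.0% | 87.7% | 92-93% | 87-88% |
| 0.50 | 92.5% | 98.0% | 91.0% | 95-96% | 91-92% |
| 0.55 | 97.7% | 99.1% | 95.0% | 98% | 96% |

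At a true OS equal to the historical 28.6%, the unconditional figure is 14.8%. The conditional figure allowing for incomplete follow-up is 46-54% (from 45.1%) or 34-39% (from 41.5%).

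**Step 4: if 13 of 31 are needed.** The printed 28.2-60.9% implies an effective n of 0.451 × 0.549/(0.327/(2 × 1.2816))² = about 15. At n = 15 the log-log interval is 28.4-60.4% and the log interval 31.3-65.0%, so that interval looks log-log. The comparison at OS 0.30 is then 10.7% unconditional against 30-36% (from 45.1%) or 21-24% (from 41.5%) with incomplete follow-up. Treating the 22 as complete, it is 53.7% (3 of 9 needed) or 27.0% (4 of 9).

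**Step 5: was the rule already met?** 28.2 exceeds 28 but not 28.6; 25 exceeds neither. The stated width of 0.33 matches 60.9 - 28.2 = 32.7 points, not 68 - 25 = 43 points.

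**The case against.** The plan is open about the amendment. It prints the interim OS, frames the objective as estimation, disclaims any claim of improvement, and cites Table 1 for precision. The caption correctly says 31 patients. The sample size and comparator study come from the original design, and an 80% lower bound corresponds to its one-sided alpha of 0.1. All of that stands and lowers the severity. It does not remove the point, because the plan keeps a go threshold and a table of pass probabilities that the interim data contradict.

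The size of the gap is also uncertain. The 80% figure treats all 22 as complete. On the 13-survivor scale with incomplete follow-up, 21-36% is only about 1.1 to 1.8 times the printed 19.8%. Like for like, though, the reference is 10.7%, so the chance still about doubles or more.

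Three stronger readings are tempting, and the documents do not support them:
- A reader might infer that the rule was already satisfied when written. That holds only for 28.2% against the rounded 28%. It fails against Table 1's 28.6%, and the 25% bound in section 9.2.1.2 misses both.
- A reader might infer that the nine new patients can only keep or undo a pass. Section 9.2.1.2 also counts further follow-up of the first 22, and under the 28.6% threshold or the 25% bound new data could create a pass.
- A reader might infer that Table 1 understates the chance everywhere. From 41.5% on the log scale, the conditional figure is slightly lower at 0.50 and 0.55 (with 9/22 complete, 91.0% against 92.5% and 95.0% against 97.7%). With 13 needed, the simulated figure at 0.55 is lower from either interim value (about 94% or 89% against 94.9%), and from 41.5% the reversal already appears at 0.47 (about 73% against 77.1%).

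**Conclusion.** The point holds. The go rule was set with OS from 22 of its 31 patients in view, and Table 1's probabilities are not those of this trial. At a true OS of 0.30, the printed 19.8% compares with about 39-58% allowing for incomplete follow-up, or 54-80% with the 22 treated as complete, on the interval scale that reproduces Table 1. If 13 survivors are needed, 10.7% compares with about 21-36% or 27-54%. In every scenario examined at 0.30, the like-for-like chance is at least about double. At high true OS the difference is small or reversed.

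The ranges rest on an assumed follow-up pattern, an unstated interval transformation and an unresolved interim estimate. Whether the rule was already met cannot be settled from the printed figures, though the stated width favours the 28.2-60.9% interval. The section should be corrected, but the point is not critical, because the plan already declines to claim improvement.

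**What to change.** In section 9.2.1.2:
- Reconcile the interim estimate (45.1%, 28.2-60.9% against 41.5%, 25-68%) and the threshold (28% against 28.6%).
- State the interval transformation there and in section 9.3.3.
- Re-run Table 1 conditional on the 22-patient data, simulating only their remaining follow-up and the nine new patients. Failing that, label the existing table as unconditional and not this trial's pass probability.
- State that the threshold was chosen with the interim OS known.
- Report one-year OS for the first 22 and the last nine beside the pooled estimate, as description only, because nine patients give an imprecise estimate.

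The cost is a simulation re-run, revised wording, and a less favourable stated figure at low true OS. No further patients or data are needed.
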